7.9.6 Pharmacokinetic Assessments

Assessments of the PK of BSI-045B will be evaluated throughout the Treatment Period and Follow-up Period as outlined in the Schedule of Activities in Section 3. Blood sample for the analysis of the PK of BSI-045B will be collected at the time points indicated in the PK Sample Collection in Table 1 and Table 2. Refer to the laboratory manual for additional details on laboratory assessment and sample processing.

V4.0_8 Jul 2024 Page 46 of 68

^{**} Induration/Swelling should be evaluated and graded using the functional scale as well as the actual measurement.

7.9.7 Immunogenicity

Assessments of the ADA status (negative or positive with titer) of BSI-045B will be evaluated throughout the Treatment Period and Follow-up Period as outlined in the Schedule of Activities in Section 3. Blood sample for the analysis of the ADA of BSI-045B will be collected at the time points indicated in the Immunogenicity Sample Collection in Table 1 and Table 2. Refer to the laboratory manual for additional details on laboratory assessment and sample processing.

7.9.8 Pharmacodynamic Biomarker Assessments

Blood samples (4 mL) for TARC/CCL-17, periostin, and IgE concentrations will be collected at W1D1, W2, W3, W4, W8, W12, W16, W20, and W24 within 1 h before each dose during the Treatment Period, on every visit during the Follow-up Period, and at the time of early withdrawal from the study drug.

7.10 Criteria for end of Study

A patient is considered to have completed the study when study and follow-up procedures have been completed as per the Schedule of Activities.

The end of this study is defined as the date when the last patient, last visit occurs or when last patient finished the safety follow-up, whichever occurs first.

7.11 Criteria for Early Discontinuation of Study Drug

A patient has the right to withdraw from treatment at any time at his/her request and this decision will not affect the treatment provided by clinicians or research institutions in the future. Moreover, the patients may be withdrawn at any time at the discretion of the Investigators for safety, behavioral, compliance, or administrative reasons. When medically feasible, the Medical Monitor should be consulted prior to study drug discontinuation. Study drug treatment will be permanently discontinued if one of the following criteria applies:

- Withdrawal of consent
- Patient or guardian requests to discontinue the study drug
- Start of new anti-AD treatment
- Lost to follow-up
- Death
- Intolerable safety issues

V4.0_8 Jul 2024 Page 47 of 68

• AE, abnormal laboratory tests, or other medical condition (including pregnancy) occurred, and the Investigator judges that the study drug should be terminated based on the best interests of the patient

- Major noncompliance with the study protocol and in the Investigator's judgment, treatment should be discontinued
- Other conditions that the Investigator considers inappropriate for continue treatment
- Study terminated by the Sponsor

If a patient withdraws from study treatment after receiving study treatment, a safety examination is required within 7 days after the patient's withdrawal. Additional follow-up assessments should be completed.

7.12 Criteria for Withdrawal from the Study

The primary reason for withdrawal from the study will be recorded as one of the following:

- Death
- Lost to follow-up
- The patient has poor compliance and serious deviation from study protocol
- Withdrawal of consent by patient
- Study terminated by Sponsor or regulatory agency
- Other conditions as per Investigators

The Investigator or designee must make appropriate efforts to contact any patient who is lost to follow-up, with at least 3 telephone contacts. If a patient who has received study drug withdraws from the study early, a safety examination is required within 7 days after the patient's withdrawal if the patient consents to this visit.

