7.14 Compliance/Adherence

In select cases, the Investigator may need to discuss with the patient whether they should continue the study and make relevant explanations in certain situations, including but not limited to the following:

- 1) The Investigator considers it advisable for the patient to stop the study from the perspective of medical ethics, or believes that withdrawal from the study may be in the best interest of the patient.
- 2) During the study, the patient does not comply with the study plan and shows poor compliance (eg, failure to take the study drug or failure to obtain samples for PK and safety evaluation as required by the protocol).
- 3) The patient evidences behavioral issues during the study that may affect study assessments

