11.3.2 Protocol Deviations

A protocol deviation is defined as any change, divergence, or departure from the study design or procedures defined in the protocol.

An important protocol deviation is defined as a protocol deviation that might significantly affect the completeness, accuracy, and/or reliability of the study data or that might significantly affect a patient's rights, safety, or well-being. Important protocol deviations may result in the removal of patients from the study and the analysis.

Protocol deviations will be classified as important and non-important by the Sponsor and Investigators prior to database lock.

Protocol deviations will be summarized.

V4.0_8 Jul 2024 Page 61 of 68

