#### 4.7.1 Eczema Area and Severity Index (EASI)

The EASI score is a composite index that measures the severity of AD based on the average intensity of four clinical signs (erythema, edema/papulation, excoriations, and lichenification) at four body areas (head, neck, upper extremities, and trunk and lower extremities), and the percentage of affected area for each of the four body areas.

The baseline for EASI is defined as the score measured prior to dosing on Day 1.

Measured values, changes from baseline and percent change from baseline in EASI score will be summarized descriptively on scheduled visit.

The primary efficacy endpoint is the proportion of subjects with EASI75 (a 75% reduction in the EASI score) at 2 weeks after last dose at Week 24. The exploratory endpoints include the proportion of subjects achieving EASI90 at Weeks 26 (2 weeks after last dose at Week 24), the proportion of patients with EASI50 at Week 26 (2 weeks after last dose at Week 24). The corresponding 95% two-sided confidence intervals (CIs) will be calculated using the exact binomial distribution and presented for EASI75, EASI90, and EASI50.

For primary analysis, the percent change from baseline in EASI score, EASI50, EASI75, EASI90 in the EASI score will be calculated with observed data. If the subject has missing value for EASI at scheduled visit, the subject will be excluded from the calculation of proportion at specify visit.

Mean (±standard deviation) of the percent change from baseline in EASI score with observed data will be plotted at scheduled visit.

For sensitivity analysis, the missing value will also be imputed with last observation carried forward (LOCF) method. The imputed data for the percent change from baseline in EASI score will be summarized descriptively on scheduled visit. The proportion of subjects with EASI50, EASI75 and EASI90 at 2 weeks after last dose at Week 26 will also be calculated with imputed data.

A listing of all EASI score will be provided by subject number.

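### The protocol does not separate stopping study drug from leaving the study for noncompliance or deviations, so patients who could still be scored may have no Week 26 EASI

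*Protocol*

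**What the plan says.** Protocol 7.11 concerns stopping study drug. Its list includes "Major noncompliance with the study protocol and in the Investigator's judgment, treatment should be discontinued", and for patients who stop treatment it asks for a safety examination within 7 days and adds "Additional follow-up assessments should be completed". The same section says that "the patients may be withdrawn at any time at the discretion of the Investigators for safety, behavioral, compliance, or administrative reasons", without stating whether this means withdrawal from the drug or from the study.

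Protocol 7.12 concerns leaving the study. The reasons to be recorded include "The patient has poor compliance and serious deviation from study protocol" and "Other conditions as per Investigators". What it requires afterwards is a safety examination within 7 days if the patient agrees; it has no counterpart to the follow-up sentence in 7.11.

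Two other sections bear on the same decision. Protocol 7.14 lets the investigator discuss with a patient whether to continue the study, and gives as an example of poor compliance "failure to take the study drug or failure to obtain samples for PK and safety evaluation as required by the protocol". Protocol 11.3.2 states: "Important protocol deviations may result in the removal of patients from the study and the analysis".

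On the analysis side, the primary endpoint is the EASI75 proportion at Week 26. Under SAP 4.7.1 the primary analysis uses observed data, and if the EASI is missing at a scheduled visit "the subject will be excluded from the calculation of proportion at specify visit". LOCF is a sensitivity analysis. Protocol 7.9.3 and Table 2 call for an EASI at early withdrawal. Protocol 7.15 states that the study is neither randomized nor blinded.

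**The concern.** The same behaviour can lead down two routes. On one, the patient stops drug and follow-up continues. On the other, the patient leaves the study after a single safety visit. No rule says which applies, and the choice can rest with an investigator who knows how the patient is doing. A missed PK sample or an important deviation does not prevent anyone from scoring an EASI at Week 26, so a score lost this way is lost by choice.

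If patients who are doing poorly are also the ones who comply less, which is plausible because Protocol 9.4 permits no rescue medication, the exits would tend to be non-responders and the observed proportion would rise. There is no control arm to share the loss. Protocol 5.4 says the findings will be used to design Phase 2b, so the EASI75 rate will be relied on even though the study is descriptive.

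**Working it through.** **1. The plan's own precision figures.** Protocol 11.1 and SAP 2.3 give maximum one-sided 95% widths of 21% (n = 20) and 19% (n = 24). Take the exact (Clopper-Pearson) lower limit L(x, n), the 5% quantile of a Beta(x, n − x + 1) distribution, and maximise x/n − L over x.

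- n = 20: maximum 20.8%, at x = 13, which rounds to 21%.
- n = 24: maximum 18.8%, at x = 16, which rounds to 19%.

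Both reproduce with every patient scored. Protocol 7.3 replaces only patients who do not complete the first five doses, so later exits reduce the number scored. From 20 patients the width becomes 22.1% with 18 scored and 23.6% with 16. From 24 it becomes 19.7% with 22 and 20.8% with 20.

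**2. Effect on the primary proportion.** The documents give neither an expected response rate nor an expected number of compliance exits, so both are assumed. Let x be the responders among n patients and k the number lost before Week 26. If all k are non-responders, the observed-case rate is x/(n − k), against x/n had they been scored. With x = 8 and n = 20:

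| Lost (k) | Observed rate | Exact one-sided 95% lower limit | Exact two-sided 95% CI |
|---|---|---|---|
| 0 | 8/20 = 40.0% | 21.7% | 19.1% to 63.9% |
| 2 | 8/18 = 44.4% | 24.4% | 21.5% to 69.2% |
| 3 | 8/17 = 47.1% | 26.0% | 23.0% to 72.2% |
| 4 | 8/16 = 50.0% | 27.9% | 24.7% to 75.3% |

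Both intervals are shown because the protocol specifies a one-sided interval and the SAP a two-sided one. With n = 24, 8/24 = 33.3% becomes 8/22 = 36.4% after two losses and 8/20 = 40.0% after four. Across both sample sizes and assumed response rates of about 30% to 60%, two losses add 2.7 to 6.7 points and four add 5.8 to 15.0.

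**3. The other direction.** If the k patients lost are responders, the rate is (x − k)/(n − k). From 8/20, that is 6/18 = 33.3% after two losses and 4/16 = 25.0% after four.

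**4. What the SAP already expects.** SAP 4.1.4 maps off-drug follow-up visits to analysis weeks. In its example the last dosing visit is Week 14 and the sixth follow-up visit, 12 weeks later, becomes Week 26 (14 + 12 = 26). Off-drug scores are therefore already meant to reach the primary timepoint, provided the patient stays in the study. A patient whose last dose is earlier finishes the 12-week follow-up before Week 26 (for example, 10 + 12 = Week 22).

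**The case against.** Much of the case on the other side stands, and it limits the point.

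- **The 7.12 item is narrower than it may look.** A reader might infer that 7.12 orders removal for poor compliance or a deviation. It joins the two with an and, sits in a list of reasons to be recorded, and names no decision-maker. The route rests on 7.11, 7.14, 11.3.2 and the open-ended item in 7.12 taken together. Deleting the compliance item alone would leave that route open and hide such exits under another code.
- **A last score is due.** A reader might infer that these patients leave unscored. An EASI is required at early withdrawal, and LOCF can use it. It is still not a Week 26 score and does not enter the primary proportion.
- **The illustrated rise depends on SAP 4.7.1.** Under the same assumption, counting missing patients as non-responders returns exactly 8/20. What no analysis can restore is the score itself. The size given here should not be added to that of any separate point about missing-data handling.
- **Some losses are unrelated.** Patients who skip visits lack scores whatever 7.12 says, and starting new AD therapy is a 7.11 reason to stop drug, not in itself a study exit.
- **Keeping patients has its own risk.** Someone who stops drug and starts another therapy could be scored as a responder, and the SAP has no rule for such scores.
- **The study is descriptive.** No hypothesis is tested and a randomized Phase 2b is planned. That lowers the stakes, but the EASI75 rate remains the primary efficacy result.

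**Conclusion.** The point holds as a gap in trial conduct. The protocol does not keep stopping drug apart from leaving the study where the ground is noncompliance or a deviation, and patients who leave before Week 26 drop out of the primary proportion. On assumed figures of 8 responders among 20 patients and two to four non-responders lost, the rate moves from 40.0% to between 44.4% and 50.0%. If responders are lost, it moves down.

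The documents do not support a claim that the rate will be inflated, or that investigators would use these provisions to remove patients who are doing badly. They give no expected number of such exits. They also do not say who scores the EASI: 7.9.3 names the investigator as rater for the IGA and facial IGA only. What they do show is an avoidable source of missing primary data that is left to discretion in an unblinded trial.

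**What to change.** - **Protocol 7.12 and 7.14:** state that noncompliance, a protocol deviation, or investigator discretion on those grounds can lead at most to stopping study drug as 7.11 already provides, and not to leaving the study. Such patients continue the scheduled efficacy visits through the Week 26 EASI unless they withdraw consent, are lost to follow-up or die. Say explicitly that an EASI visit at Week 26 applies even when the 12-week follow-up would end sooner.
- **Protocol 7.11:** make clear that the investigator-discretion sentence, so far as it concerns compliance, refers to study drug.
- **Reason code:** the compliance item may stay, to record why drug was stopped.
- **Protocol 11.3.2:** let important deviations affect only membership of the per-protocol set, not study participation or the Efficacy Analysis Set. This matches SAP section 3, where only the per-protocol set depends on deviations, and SAP 4.7, which uses that set for sensitivity. Removing only the reference to the study would not be enough, because the sentence would still allow removal from the analysis.
- **SAP 4.7.1:** flag Week 26 scores obtained after new AD therapy and state in advance how they count. Concomitant medications are already recorded throughout, so no new data are needed.

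The cost is wording and a few off-drug EASI visits, most of them already scheduled. Poorly adherent patients stay in the main estimate and may lower it; scores after new therapy may raise it, which is why they need flagging.

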7.13 Data Handling for Patients who do not Complete the Study

Before descriptive statistical analysis of data, the Investigator and the Sponsor will determine whether individual patients are to be included in a per-protocol analysis for the analysis of the primary efficacy endpoint. Patients who receive any amount of study drug will be included in safety analyses.

V4.0_8 Jul 2024 Page 48 of 68

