7.9.3 Efficacy

Patients will be assessed to determine an EASI score at Screening, prior to dosing on Day 1 (baseline), at subsequent visits, and at the time of early withdrawal from the study.

The EASI score is a composite index that measures the severity of AD based on the average intensity of four clinical signs (erythema, edema/papulation, excoriations, and lichenification) at four body areas (head, neck, upper extremities, and trunk and lower extremities), and the percentage of affected area for each of the four body areas (Hanifin and Rajka, 1980). The primary efficacy endpoint is the proportion of patients with ≥EASI75 at Week 26 (2 weeks after last dose at Week 24).

The IGA and facial IGA require the Investigator to rate the severity of AD on a scale from 0 (clear) to 4 (severe).

The assessment tool for itching is the PP-NRS, on which the patient rates the maximum severity of the itch from AD on a scale from 0 (no itch) to 10 (worst itch imaginable) over a

V4.0_8 Jul 2024 Page 43 of 68

24-hour period. The baseline PP-NRS score is based on the average of daily PP-NRS scores for the 7 days immediately preceding Day 1. Patients will complete the rating scale daily using the patient diary beginning on Day -8, throughout the last study visit, and at the time of early withdrawal from the study. In order to calculate an average for the score, the patient must have completed the diary for a minimum of 4 days during the previous 7 days.

Exploratory efficacy and safety assessments will include the following. At each visit, the percentage of patients who achieve 50%, 75%, and 90% improvement in the EASI score from Day 1) and the change in EASI score from Day 1 will be calculated. Detailed analysis of all exploratory endpoint is described in the Statistical Analysis Plan (SAP).

- Proportion of patients with EASI90 at Week 26 (2 weeks after last dose at Week 24)
- Proportion of patients with EASI50 at Week 26 (2 weeks after last dose at Week 24)
- Percent change from baseline in EASI at each visit
- Proportion of patients achieving IGA 0 or 1 Week 26 (2 weeks after last dose at Week 24)
- Percent changes in PP-NRS scores at Week 26 (2 weeks after last dose at Week 24)
- Proportion of patients achieving Facial IGA 0/1 at Week 26 (2 weeks after last dose at Week 24)
- Occurrence of conjunctivitis

7.9.4 *Safety*

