7.15 Randomization and Blinding

The study will not be randomized and will be unblinded.

V4.0_8 Jul 2024 Page 49 of 68

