#### 3. Analysis Population

The statistical analysis sets involved in this study are as follows:

**Enrolled Population:** including all subjects who sign informed consent form and are successfully screened.

**Safety Analysis Set:** including all the subjects who received at least one dose of the study drug. This analysis set will be used for analysis of safety endpoint.

Efficacy Analysis Set: including all the subjects who received at least one dose of the study drug and have undergone at least one post-baseline efficacy assessment. This analysis set will be used for analysis of efficacy endpoint.

Per protocol analysis set: a subset of efficacy analysis set of patients without any importance protocol violation, as defined by the sponsor prior to the data base locked (adhere to ICH E3 guidance) Important protocol deviations are a subset of protocol deviations that might significantly affect the completeness, accuracy, and/or reliability of the study data or that might significantly affect a subject's rights, safety, or well-being. For example, important protocol deviations might include enrolling subjects in violation of key eligibility criteria designed to ensure a specific subject population or failing to collect data necessary to interpret primary endpoints, as this may compromise the scientific value of the trial.

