#### 4.7 Efficacy Analysis

Efficacy analysis will be summarized in efficacy analysis set. As a sensitivity analysis, the per protocol population will also be assessed.

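### Per-protocol membership in this open-label trial may be decided with post-baseline EASI in view; this mainly exposes the sensitivity result, and protocol 11.3.2 must be reconciled with the SAP

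*Protocol*

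**What the plan says.** - **Protocol 7.13**, under a heading about patients who do not complete the study, states: "Before descriptive statistical analysis of data, the Investigator and the Sponsor will determine whether individual patients are to be included in a per-protocol analysis". The analysis meant is that of the primary efficacy endpoint. The section gives no criteria.
- **Protocol 11.3.2** has the sponsor and investigators sort deviations into important and non-important before database lock. It then says: "Important protocol deviations may result in the removal of patients from the study and the analysis". It does not say which analysis.
- **Protocol 7.15**: "The study will not be randomized and will be unblinded". Under 7.9.3, EASI is taken "prior to dosing on Day 1 (baseline), at subsequent visits, and at the time of early withdrawal from the study". No masked assessor is described.
- **SAP 3** builds the per-protocol set from Efficacy Analysis Set patients who have no important violation, "as defined by the sponsor prior to the data base locked". It defines importance in general terms and gives two examples, not a closed list. The Efficacy Analysis Set itself needs only one dose and one post-baseline efficacy assessment.
- **SAP 4.7** summarises efficacy in the Efficacy Analysis Set and adds: "As a sensitivity analysis, the per protocol population will also be assessed".

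**The concern.** Fixing analysis sets before lock protects a trial when those who decide cannot connect a patient with treatment or result. Here everyone receives the drug, so only the result remains to be hidden, and it accrues openly visit by visit.

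The per-protocol rate is the planned population check on the primary rate. If membership can depend on response, agreement between the two sets reassures nobody, and a higher per-protocol rate may be selection. There is no control arm, SAP 4.1.1 plans no hypothesis test, and the sponsor's plan for a Phase 2b trial is conditional on this study succeeding. The responder proportion and its checks are therefore the main efficacy evidence.

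**Working it through.** **Step 1. Who can know the outcome when deviations are classified.** The investigator rates IGA (protocol 7.9.3) and verifies the CRF data (12.3), and so has the patient's scores. The sponsor's representatives may periodically audit all CRFs before, during and after the study (12.6). This shows that the sponsor can see EASI, not that it has. Week 26 is the first follow-up visit, 2 weeks after the last dose, and the last follow-up visit is at 12 weeks. Each completer's Week 26 result is therefore on record 12 − 2 = 10 weeks before that patient's last visit. A pre-lock deadline hides nothing.

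**Step 2. Which result can move.**

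| | Protocol | SAP |
|---|---|---|
| Deciders | Investigator and sponsor (7.13, 11.3.2) | Sponsor (3) |
| Timing | Before descriptive analysis (7.13); before lock (11.3.2) | Before lock (3) |
| Effect of an important deviation | May leave the study and the analysis (11.3.2) | Leaves the per-protocol set only (3) |
| Role of per-protocol | For the primary endpoint, role not stated (7.13) | Sensitivity (4.7) |
| Classified without sight of efficacy data | Not required | Not required |

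Under the SAP, a deviation changes the per-protocol rate and leaves the main rate alone. The main rate is reached only if 11.3.2 is applied literally. Its mention of removal from the study belongs to the same wording: a patient taken off before Week 26 has no Week 26 EASI, and SAP 4.7.1 drops patients with a missing score from that visit's proportion.

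**Step 3. The plan's own precision figures.** The exact one-sided 95% lower limit for x responders of n is L = the 5% quantile of Beta(x, n − x + 1). The width is x/n − L, maximised over x.

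- n = 20: maximum at x = 13, width 20.8%, stated as 21%.
- n = 24: maximum at x = 16, width 18.8%, stated as 19%.

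Both figures reproduce.

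**Step 4. Illustration of selective exclusion.** The responder counts and numbers excluded are assumptions, and every excluded patient is taken to be a non-responder. With k excluded, the rate is x/(n − k) and the shift is xk/[n(n − k)]. Cells show the rate, with the one-sided lower limit in brackets.

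| n | x | k = 0 | k = 2 | k = 3 |
|---|---|---|---|---|
| 20 | 6 | 30.0% (14.0%) | 33.3% (15.6%) | 35.3% (16.6%) |
| 20 | 8 | 40.0% (21.7%) | 44.4% (24.4%) | 47.1% (26.0%) |
| 20 | 10 | 50.0% (30.2%) | 55.6% (34.1%) | 58.8% (36.4%) |
| 24 | 7 | 29.2% (14.6%) | 31.8% (16.0%) | 33.3% (16.8%) |
| 24 | 10 | 41.7% (24.6%) | 45.5% (27.1%) | 47.6% (28.6%) |
| 24 | 12 | 50.0% (31.9%) | 54.5% (35.3%) | 57.1% (37.2%) |

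The smallest shift is 7 × 2/(24 × 22) = 2.7 points and the largest is 10 × 3/(20 × 17) = 8.8 points. For 8/20 the shifts are 4.4 and 7.1 points.

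If exclusions are unrelated to response, no drift is expected: from 8/20, dropping 2 responders and 3 non-responders leaves 6/15 = 40%. The limits follow protocol 11.2 (one-sided). SAP 4.7.1 plans two-sided 95% intervals, whose lower limits for 8/20, 8/18 and 8/17 are 19.1%, 21.5% and 23.0%, the same pattern.

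**The case against.** The strongest reply is that the SAP already contains most of this. Protocol 11.2 and 11.4 leave analysis detail to the SAP, which is dated 13 September 2024, after protocol V4.0 of 8 July 2024. Its main set has no deviation exclusion, and per-protocol is a sensitivity analysis. This stands, and it limits the point. A reader might infer that the headline EASI75 rate is open to selection; the SAP does not support that.

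A reader might also infer unrestricted choice, patient by patient. SAP 3 ties membership to an important violation, so the choice is bounded, although what counts as important remains a judgement. The heading of 7.13 could confine its sentence to non-completers, but the route through 11.3.2 and SAP 3 covers everyone.

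Nor is timing the only safeguard. SAP 4.2 requires reasons for exclusion from each set, 4.3 a listing of all deviations by subject, and 4.7.1 a listing of all EASI scores. With 20 to 24 patients, a reader of the report could see who was left out and recompute the rate. This exposes selection after the event but does not prevent it.

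Finally, the shifts in step 4 are a worst case in one direction and sit well inside the planned 19 to 21 point width. No test or success threshold depends on them. That is correct. They show how far a check on 20 patients can drift, not what will happen.

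**Conclusion.** The point holds in limited form. The plan permits per-protocol exclusions to be decided by people who can know the patient's response, and no rule in either document prevents it. The exposure is mainly the sensitivity result. Over the assumed cases, 2 or 3 exclusions confined to non-responders move it by about 3 to 9 points (40% to 44% or 47% for 8/20). The main rate is exposed only through the unreconciled wording of 11.3.2.

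The documents do not show that the sponsor has seen each patient's EASI, or that any exclusion has followed or will follow response. The conclusion rests on the open-label design and on the absence of an outcome-free classification step. The change is worth making because it is nearly free.

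**What to change.** 1. **Protocol 11.3.2 and 7.13.** In 11.3.2 delete the words *and the analysis*, and state that a deviation never removes a patient from the Efficacy Analysis Set. Align 7.13 with SAP 3 and 4.7: per-protocol is sensitivity only, with the same deciders and the same timing throughout.
2. **Classification.** Classify important deviations from a listing that omits post-baseline EASI, IGA and PP-NRS, without the vote of the investigator who scored the patient. Sign it off, with date and reason for each exclusion, before the Week 26 responder table is run. This reduces the risk but does not blind anyone who already knows the scores.
3. **SAP 3.** Prespecify per-protocol exclusions on baseline or eligibility breaches, such as washout shortfall or unmet EASI, IGA or BSA entry criteria. Do not exclude automatically for post-baseline events that can result from non-response, such as AD-active medication or stopping early, or else report those exclusions separately. SAP 4.1.4 maps follow-up visits after early stopping onto the week schedule (a last dose at Week 14 gives visits up to Week 26). Early stoppers can therefore count in the primary denominator, and excluding them could itself raise the per-protocol rate.

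The cost is protocol and SAP wording and one listing with columns left out; no visits or patients are added. The downside is slightly less freedom to handle unforeseen deviations. These edits do not settle how a patient withdrawn from the study before Week 26 is counted. That is a missing-data question under SAP 4.7.1.
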